5.3 Exploratory Endpoints

Not Applicable.

5.4 Safety Endpoints

- Intra- and perioperative implant-related “Adverse Events” (AE) and complications until discharge
- Postoperative AE up to 10 years after the surgery

6 STATISTICAL CONSIDERATIONS

6.1 Determination of Sample Size

A minimum of 225 patients were planned to be enrolled at all investigational sites.

6.2 Randomisation

Not Applicable.

CONFIDENTIAL AND PROPRIETARY

This document contains information that is confidential and proprietary to Smith & Nephew PLC and Smith & Nephew, Inc. and is intended for use only by Smith+Nephew and its manufacturer. It shall not be reproduced or copied in whole or in part, nor shall the contents be disclosed by any means without prior written permission from Smith+Nephew, nor shall anyone make any use of it that is contrary to the expressed or implied wishes of Smith+Nephew.

Statistical Analysis Plan

Multicenter Clinical Observation Using the Cementless Version of the POLARSTEM™

Number: D10070
ST: 1133
Version: 1.0, 30-Nov-2021
Page: 8 of 19

6.3 Interim Analysis

Interim analyses were planned and carried out for this study at 5 year follow-up. The outcome from the analyses has previously been reported.

7 STATISTICAL ANALYSIS

7.1 General

Smith & Nephew's Global Biostatistics group will conduct the statistical analysis for this study. Unless otherwise stated, all significance tests and hypothesis testing will be two-sided, performed at the 5% significance level. Resulting p-values will be quoted and 95% two-sided confidence intervals will be generated where appropriate. All p-values will be rounded to three decimal places, p-values less than 0.001 will be presented as '<0.001' in all tables.

Baseline data, outcome variables and adverse events will be summarized according to the nature of the variable. Categorical and ordinal variables will be summarized with frequencies and percentages. Continuous variables will be summarized with the following summary statistics: number of observations, mean, median, standard deviation, minimum and maximum values. The outcome variables will be summarized for all recorded time points.

Appropriate parametric and/or non-parametric analyses will be chosen for statistical analysis. The analysis of continuous variables will be done using a paired-sample t-test if appropriate, to test for differences between the baseline and end of study outcomes. The Wilcoxon rank-sum tests will be explored if the data is non-normal.

If data allows, Kaplan-Meier estimates will be calculated for the survival data otherwise only the survival proportion with a 95% confidence interval will be reported..

All analyses will be performed in SAS version 9.4 (or later).

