3 STUDY DESIGN

The study is a prospective long-term multicenter clinical observation study. Overall a minimum of 225 patients were enrolled consecutively into the study at 3 sites. Patients enrolled into the study had at least one of the following indications:

- Primary or Secondary coxarthrosis
- Rheumatoid arthritis
- Developmental dysplasia of the hip
- Fracture or avascular necrosis of the femoral head

The patients were enrolled consecutively over 12 months and followed up for 10 years with observations at 3 months, 1 year, 3 years, 5 years and 10 years.

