7.4 Derived Data

The following variables will be derived from the collected data:

- ❖ **Age:** The age will be calculated as the exact number of days between the date of birth and date of entry into study converted to years (i.e. difference in days/365.25).
- ❖ **Body Mass Index (BMI):** BMI is obtained by dividing the weight (kg) at enrollment by the square of height (m) i.e. weight (kg)/ height² (m).

CONFIDENTIAL AND PROPRIETARY

This document contains information that is confidential and proprietary to Smith & Nephew PLC and Smith & Nephew, Inc. and is intended for use only by Smith+Nephew and its manufacturer. It shall not be reproduced or copied in whole or in part, nor shall the contents be disclosed by any means without prior written permission from Smith+Nephew, nor shall anyone make any use of it that is contrary to the expressed or implied wishes of Smith+Nephew.

Statistical Analysis Plan

Multicenter Clinical Observation Using the Cementless Version of the
POLARSTEM™

Number: D10070
ST: 1133
Version: 1.0, 30-Nov-2021
Page: 10 of 19

- ❖ **Baseline:** Preoperative examination visit is considered as the baseline visit for all parameters for which data is collected at that time point.
- ❖ **Safety population indicator variable:** A binary variable will be defined if the patient receives study treatment then the patient is included in the safety population or not. Only patients indicated as included in the safety population will be used in the safety population analysis.
- ❖ **FAS set indicator variable:** A categorical variable will be defined to indicate if the patient receives study treatment and attends at least one post-baseline assessment then the patient is included in the full analysis set. Only the patients in the included category will be included in the full analysis set.
- ❖ **Per-protocol set indicator variable:** A categorical variable will be defined to indicate if the patient is in the full analysis set and have no significant protocol deviations and meet the inclusion/exclusion criteria. Only the patients in the included category will be included in the per-protocol analysis set.
- ❖ **Visit Interval:** days between baseline assessment and Study Visit defined as: Date of Study Visit – date of baseline assessment.
- ❖ **Survival time (days):** End of study/Death/Loss to Follow-up/revision date – baseline assessment date+1; In months, divide days by 30.4375; In years, divide days by 365.25.

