7.11 Analysis of Secondary Endpoints

- Harris Hip Score (HHS)

CONFIDENTIAL AND PROPRIETARY

This document contains information that is confidential and proprietary to Smith & Nephew PLC and Smith & Nephew, Inc. and is intended for use only by Smith+Nephew and its manufacturer. It shall not be reproduced or copied in whole or in part, nor shall the contents be disclosed by any means without prior written permission from Smith+Nephew, nor shall anyone make any use of it that is contrary to the expressed or implied wishes of Smith+Nephew.

Statistical Analysis Plan

Multicenter Clinical Observation Using the Cementless Version of the POLARSTEM™

Number: D10070
ST: 1133
Version: 1.0, 30-Nov-2021
Page: 17 of 19

- HOOS Score (Hip Dysfunction and Osteoarthritis Outcome Score), which includes the complete WOMAC Osteoarthritis Index
 - The different dimensions of and the overall HHS, and WOMAC from HOOS scores at all recorded time points and end of study will be summarized using mean, median, SD, minimum, and maximum. A paired sample t-test (or a non-parametric equivalent such as the Wilcoxon signed-rank test) will be used to test the difference between preoperative and postoperative scores.
- Radiological: At all recorded time points (from the perioperative through the 10 year postoperative follow-up), the following analyses would be carried out:
 - For general findings: At the acetabulum position, cranial migration (mm), medial migration (mm) and tilted angle would be summarized using descriptive characteristics for continuous variables; At the stem position, varus tilting, valgus tilting and sunken (mm) will be summarized using descriptive statistics for continuous variables; Integration in general/acetabulum, integration in general/stem and ectopic ossification will be summarized using descriptive statistics for categorical variables.
 - Within the cup and the stem (by zone): The number and percent of hips with osteolysis will be summarized; for seams (0mm, 1mm, 2mm &>2mm), atrophy (none, mild, moderate & severe) and hypertrophy (none, mild, moderate & severe) their frequencies (n) and percentages will be presented.

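### SAP 7.1 names the Wilcoxon rank-sum test, an independent-samples test, as the fallback for a paired comparison for which SAP 7.11 names the signed-rank test

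*SAP*

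**What the plan says.** SAP 7.1 General sets the default for continuous outcomes: "The analysis of continuous variables will be done using a paired-sample t-test if appropriate, to test for differences between the baseline and end of study". The next sentence gives the alternative: "The Wilcoxon rank-sum tests will be explored if the data is non-normal".

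SAP 7.11, on HHS and the WOMAC scores derived from HOOS, states: "A paired sample t-test (or a non-parametric equivalent such as the Wilcoxon signed-rank test) will be used to test the difference between preoperative and postoperative".

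Both sections compare the same patients at two times. SAP 7.4 fixes the first of them: "Preoperative examination visit is considered as the baseline visit for all parameters for which data is collected at that time point". SAP 7.1 also sets the benchmark for any p-value: "all significance tests and hypothesis testing will be two-sided, performed at the 5% significance level".

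**The concern.** The paired t-test works on within-patient differences. Its usual rank-based counterpart is the signed-rank test. The rank-sum test treats the two visits as separate groups of patients, so its standard error ignores the correlation between a patient's two scores, and its p-value is correct only if that correlation is zero.

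The fallback could plausibly be needed. The scores are bounded and some are coarse: in SAP 7.4 the HHS pain item takes six values, range of motion runs from 0 to 5, absence of deformity is 0 or 4, and raw WOMAC stiffness runs from 0 to 8. SAP 7.11 covers the separate dimensions as well as the totals. SAP 7.1 is also the only place that says when to leave the t-test, namely when data are non-normal, and there it names the unsuitable test. A programmer who took 7.1 literally could run the wrong analysis and still claim to have followed the plan.

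**Working it through.** **Could the rank-sum sentence refer to something else?** SAP 3 describes one observed cohort ("The study is a prospective long-term multicenter clinical observation study"), SAP 6.2 gives randomisation as not applicable, and the SAP specifies no comparison between independent groups. The sentence can only refer to the paired comparison that precedes it.

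**Where would it act?** Survival is estimated by Kaplan-Meier with confidence intervals (SAP 7.10). Radiological, baseline and safety data are summarised descriptively (SAP 7.11, 7.5, 7.13). The preoperative versus postoperative HHS and WOMAC comparison is the only significance test that the SAP assigns to an endpoint.

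**Inputs.**
- Level: two-sided 0.05 (SAP 7.1).
- Pairs: 225 subjects implanted (SAP 7.15) and 30% drop-out over 10 years (Protocol 2.2), so 225 × 0.70 = 157.5, about 157 pairs.
- Assumed, because the documents do not give them: within-patient correlation ρ from 0.2 to 0.7, and shifts in units of the SD of a single score.

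The plan states no power or p-value for this comparison, so there is no figure of its own to reproduce.

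**Type I error of the rank-sum test on paired data.** With bivariate normal scores, the correlation between the ranks is ρ_s = (6/π)·arcsin(ρ/2). The standardised rank-sum statistic then has large-sample variance 1 − ρ_s instead of 1, so

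true size = 2·[1 − Φ(1.96/√(1 − ρ_s))].

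For ρ = 0.5: ρ_s = 0.483, √(1 − 0.483) = 0.719, 1.96/0.719 = 2.73, size 0.006.

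**Power.** Simulated with 157 normal pairs and a shift of 0.2 SD, 8,000 runs per setting.

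| ρ | true size, rank-sum | power, rank-sum | power, signed-rank |
|---|---|---|---|
| 0.2 | 0.029 | 0.39 | 0.48 |
| 0.3 | 0.020 | 0.39 | 0.54 |
| 0.5 | 0.006 | 0.37 | 0.68 |
| 0.7 | 0.0005 | 0.34 | 0.88 |

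Simulation under the null (20,000 runs; 100, 157 and 225 pairs) agreed with the size formula. The signed-rank test held 0.047 to 0.053 throughout. At ρ = 0 the rank-sum size is 0.05. At ρ = −0.3, not the expected case, it would be 0.084.

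**Skewed scores.** With log-normal margins (8,000 runs per setting), rank-sum size was 0.029 to 0.032 at ρ = 0.2, 0.006 to 0.008 at 0.5 and 0.0004 to 0.001 at 0.7, so the pattern does not depend on normality. Here ρ is the correlation on the log scale.

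**Larger shifts.** With 150 pairs and 0.3 SD, power was 0.73 against 0.80 at ρ = 0.2 and 0.79 against 0.95 at ρ = 0.5. At 0.5 SD both tests reached at least 0.99 for ρ from 0.2 to 0.7. With only 100 pairs and ρ = 0.3, 0.5 SD gave 0.96 against 0.99, and 1 SD gave rejection in every run with either test.

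**The case against.** The best defence is that SAP 7.11 already settles the matter. It is the endpoint-specific text, it says its test will be used, and it covers the only hypothesis tests that the SAP assigns. SAP 7.1 says only that rank-sum tests will be explored, and also that appropriate analyses will be chosen. The phrase "a non-parametric equivalent such as the Wilcoxon signed-rank test" means equivalent to a paired t-test, which the rank-sum test is not, so the words *such as* do not let it in. On this view 7.1 contains a naming slip.

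Most of this stands. A reader might infer from 7.1 that the trial will report wrong p-values. The documents do not support that: it happens only if the general sentence is followed over the specific one. A reader might also take a missed 5% level to mean false claims of benefit. With positive correlation the reverse holds: p-values are too large and small changes are missed.

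The size of the loss also depends on assumed values. At correlation 0.2, or with shifts above 0.3 SD, the gap is modest or absent. Carrying observations forward (SAP 7.3) could bring the number of pairs nearer 225.

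What the defence does not remove is that 7.1 names a test that does not fit the design, and no rule says which section prevails.

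**Conclusion.** SAP 7.1 is wrong as written and disagrees with 7.11; the correction is minor. If 7.1 were followed, the rank-sum p-values would be invalid whenever a patient's two scores are correlated. Under positive correlation the consequence is conservatism and lost power, and it matters mainly for shifts of roughly 0.2 to 0.3 SD with moderate to high correlation. These sizes rest on assumed correlations and shifts.

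The effect is confined to HHS and WOMAC. SAP 5.2 lists these as secondary endpoints, although SAP 4.1 places their evaluation among the primary objectives. No success criterion hangs on their p-values, and the survival primary endpoint (SAP 5.1) is unaffected. The documents therefore do not support treating this as a threat to the trial's main conclusion.

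**What to change.** In SAP 7.1, replace *Wilcoxon rank-sum tests* with *Wilcoxon signed-rank test* on the paired preoperative-postoperative differences, so that 7.1 and 7.11 name the same test. This is a wording change, with no new data and no change of design. Whether the hip or the patient is the unit for bilateral cases is a separate question that this edit does not settle.

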7.2 Analysis Populations

All subjects who provide informed consent are considered study participants. Study populations are defined as follows:

CONFIDENTIAL AND PROPRIETARY

This document contains information that is confidential and proprietary to Smith & Nephew PLC and Smith & Nephew, Inc. and is intended for use only by Smith+Nephew and its manufacturer. It shall not be reproduced or copied in whole or in part, nor shall the contents be disclosed by any means without prior written permission from Smith+Nephew, nor shall anyone make any use of it that is contrary to the expressed or implied wishes of Smith+Nephew.

Statistical Analysis Plan

Multicenter Clinical Observation Using the Cementless Version of the POLARSTEM™

Number: D10070
ST: 1133
Version: 1.0, 30-Nov-2021
Page: 9 of 19

- **Full analysis population (FAS)**, including all subjects that were included in the study, who received study treatment and attended at least one post baseline assessment.
- **Per protocol analysis population**, including all subjects in the full analysis population, have no significant protocol deviations and meet the inclusion/exclusion criteria.
- **Safety population**, including all subjects who have received study treatment.

Statistical analysis will be performed using each of the subject populations as follows: Analysis of primary, secondary and exploratory variables will be performed separately using both the FAS and the Per-Protocol Set. All safety analyses will utilise the Safety Population. Demographic characteristics will be summarized for each analysis population. Demographic characteristics will be summarized on a subject level. For bilateral subjects the data corresponding to the date of the hip's first enrolment into the study will be used.

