1.3 Objectives

The goal of this multicenter clinical observation is to validate short-, mid-, and long-term outcome (efficacy and safety) of the POLARSTEM®.

Efficacy evaluations

- Evaluation of function, range of motion (ROM) and pain as assessed by Harris Hip Score, Hip disability and osteoarthritis outcome score (HOOS) [7, 8], an extension of the Western Ontario and McMaster Universities Osteoarthritis Index (WOMAC).
- Radiographic changes as defined by radiolucent lines, osteolysis, hypo- and hypertrophy, implant loosening or migration

Safety evaluations

- Intra- and perioperative device-related adverse events (AE) and complications up to discharge
- Postoperative AE up to 10 years

Long-term survivorship will be calculated according to Kaplan-Meier with stem revision due to any reason as endpoint.

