3.4 Complications/adverse events/lost-to follow-up

Complications and adverse events are noted at each follow-up interval. For completed observations due to death of the patient, explantation of the device or patient's address unknown the latest status will be recorded as an endpoint. Patients will be considered lost to follow-up after they have missed two visits and all attempts to locate and evaluate them have failed. Patients who refuse to attend follow-up or patients unable to attend follow-up will be assessed by telephone if possible. Minimal data concerning the implant status should be acquired by telephone.

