5 STUDY ENDPOINTS

5.1 Primary Endpoint

Short term, medium term and long term survival rates at 3 months and at 1, 3, 5, and 10 years.

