7.3 Handling of Missing, Incomplete and Repeat Data

Missing and incomplete data are usually due to lost to follow-up, revision, death and patient withdrawal. A complete accountability along with the explanation for lost-to-follow-up, death, revision, and withdrawn patients will be provided in the final study report and these subjects will be treated as censored at the date of lost-to-follow up in the survival analysis. The missing due to revision will be treated as device failure. A complete assessment of the informative/non-informative missing data will be performed. In case of missing outcome values at designated time points, the last observation carried forward (LOCF) method will be used.

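### The primary survival analysis requires an undefined post-baseline attendance, which can remove stems revised before the first follow-up visit

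*SAP*

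**What the plan says.** The SAP's primary endpoint (5.1) is "Short term, medium term and long term survival rates at 3 months and at 1, 3, 5, and 10 years". The protocol (1.3) specifies Kaplan-Meier survivorship with "stem revision due to any reason as endpoint".

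SAP 7.2 sets the populations: "Analysis of primary, secondary and exploratory variables will be performed separately using both the FAS and the Per-Protocol Set". The FAS is limited to subjects "who received study treatment and attended at least one post baseline assessment". The Per-Protocol set is drawn from the FAS and so carries the same condition. The Safety population has no attendance condition, but apart from demographic summaries it is used only for safety analyses.

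SAP 7.4 repeats the rule in the FAS indicator (a treated patient who "attends at least one post-baseline assessment then the patient is included in the full analysis set") and makes no exception for revised patients. On timing it says only this: "Preoperative examination visit is considered as the baseline visit".

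SAP 7.3 says of revisions: "The missing due to revision will be treated as device failure".

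In protocol Table 1 the row after the preoperative one is the 3-month visit, at 10–14 weeks. Protocol 3.4 refers to "completed observations due to death of the patient, explantation of the device" or an unknown address, with the latest status recorded as an endpoint.

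**The concern.** In a time-to-revision analysis, entry to the analysis set should not depend on anything that the revision itself can prevent. Here it may. The SAP allows two readings of a post-baseline assessment.

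- **Reading 1: a scheduled follow-up visit.** A patient revised before 10–14 weeks who attends no later visit is outside the FAS and the Per-Protocol set. The failure is lost from both numerator and denominator. Because 3 months is itself a primary landmark, the analysis would lose the very failures that landmark should show, and every later landmark would be raised too.
- **Reading 2: an operative or perioperative assessment also counts.** Every implanted subject then qualifies. The attendance condition has no effect, and the FAS is the same as the Safety population.

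The SAP does not say which applies. Under reading 1, survival can only be biased upward by these exclusions. The primary estimate could also disagree with the report's own revision, disposition and accountability tables, where the same revisions would still appear.

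**Working it through.** The plan gives no figure for this effect, so there is none to reproduce. The check has a textual part and an arithmetic part.

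**Text: can an early revision fall out?**

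1. Survival is the primary endpoint (SAP 5.1), and primary variables go to the FAS and Per-Protocol set (7.2).
2. Both sets require an attended post-baseline assessment (7.2, 7.4), with no exception for revision.
3. The first postoperative row of protocol Table 1 is at 10–14 weeks, and protocol 3.4 treats explantation as the end of observation. An early revised patient may therefore have no follow-up visit.
4. SAP 7.3 codes revision as device failure. That determines how a subject in the analysis is counted. It does not readmit a subject whom 7.2 excludes.
5. A revised patient who attends later stays in under either reading, as does a bilateral patient seen for the other hip.

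Under reading 1 the exclusion therefore follows from the text.

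**Arithmetic: how large is it?**

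Inputs:

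- N = 225 subjects implanted (SAP 7.15).
- k = subjects revised before the first visit who attend nothing later. This is an assumption, shown from 0 to 4, because the documents give no early revision count.
- One hip per subject, and no censoring before those revisions.

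Formula: all-implanted survival = FAS survival × (1 − k/225).

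*At 3 months, with no other revision.* The FAS shows (225 − k)/(225 − k) = 100%. The all-implanted value is (225 − k)/225. Intervals are exact (Clopper-Pearson) 95%.

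| k | All implanted (95% CI) | FAS (lower 95% limit) | Overstatement, k/225 |
|---|---|---|---|
| 0 | 100% (98.37–100) | 100% (98.37) | 0 |
| 1 | 99.56% (97.55–99.99) | 100% (98.37) | 0.44 points |
| 2 | 99.11% (96.83–99.89) | 100% (98.36) | 0.89 points |
| 3 | 98.67% (96.15–99.72) | 100% (98.35) | 1.33 points |
| 4 | 98.22% (95.51–99.51) | 100% (98.34) | 1.78 points |

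At k=4 the lower FAS limit (98.34%) lies just above the all-implanted estimate (98.22%).

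*If some early-revised patients attend later.* Of four early revisions, let r attend later and stay in. FAS survival is then 221/(221 + r), and the gap to 221/225 is 1.33 points (r=1), 0.88 (r=2), 0.44 (r=3) and 0 (r=4).

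*At 10 years.* Overstatement = FAS survival × k/225. FAS survival is assumed, over the range 90–99%.

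| FAS survival at 10 years | k=1 | k=4 |
|---|---|---|
| 90% | 0.90 × 1/225 = 0.40 points | 0.90 × 4/225 = 1.60 points |
| 99% | 0.99 × 1/225 = 0.44 points | 0.99 × 4/225 = 1.76 points |

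Under reading 2 every entry is zero.

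**The case against.** The strongest counter-argument is that reading 2 may be what was meant. Baseline is the preoperative visit, so taken literally anything later is post-baseline. SAP 7.6 describes clinical follow-up as starting at the operative stage, 7.11 has a perioperative radiological time point, and complications are recorded up to discharge. That support is real, but it does not settle the matter. SAP 7.5 places operative-visit data, including early postoperative complications, under baseline data. Reading 2 would also leave the attendance condition with nothing to do beyond the requirement of having received study treatment. Reading 1 is at least as natural.

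The size is also assumed. Each unit of k needs both an early revision and no later attendance. Protocol 3.4 asks that the latest status be recorded and allows implant status to be obtained by telephone. This stands as a limit on the claim: k may be 0, and k=4 has no support in the documents. The k=4 comparison of limits has a margin of only about 0.1 point and sets one population's limit against another's estimate, so it is only an illustration. The SAP does not say whether a telephone contact or recorded status counts as attendance, which is part of the same gap.

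Early revisions would also remain visible in the accountability, disposition, revision and adverse event outputs. They would, so nothing is concealed, but those outputs do not correct the Kaplan-Meier estimate.

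Finally, a clarifying phrase could be enough. Stating that any postoperative implant status, including a revision, qualifies would remove the bias from early revision. Naming all implanted hips as the set is cleaner, because the survival denominator then depends on no attendance rule. It is right, however, that the Safety population is defined by subject, so the unit of analysis must be stated.

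**Conclusion.** The concern holds. The primary survival analysis rests on an undefined attendance condition that, on one natural reading, excludes some early failures and can bias survival only in the device's favour. On the other reading the condition has no effect. The wording needs correcting in either case.

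Under reading 1 the overstatement at 3 months is 0.44 points per excluded revision, and at 10 years it is 0.40–0.44 points per revision for FAS survival of 90–99%. This assumes 225 subjects with one hip each and no earlier censoring. The number of hips is not given, and bilateral patients are allowed. The effect is zero if k=0 or if reading 2 applies. The direction follows from the text, whereas the size cannot be fixed from the documents. This should be fixed before the final analysis; confidence is medium because the intended reading is not stated.

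**What to change.** - In SAP 7.2 and 7.10, state that survival is analysed in all implanted hips of the existing Safety population, with the hip as the unit. Every stem revision from surgery onward counts as an event, and hips without follow-up are censored at the last known implant status.
- In 7.2 and 7.4, define a post-baseline assessment, and say whether operative, discharge and telephone contacts count.
- Keep the FAS and Per-Protocol set for HHS, WOMAC and radiographic endpoints. Per-Protocol survival can remain as a supplementary analysis.
- Check the survival-time derivation in 7.4 against the new wording, since it counts from the baseline assessment date and not from surgery.

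The cost is a few sentences of SAP text and no new data. Reported survival may become slightly less favourable.
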